5.2 Pulmonary Evaluation of Subjects

In order to test the overall hypotheses and to accomplish the objectives proposed as they relate to the pulmonary system, the expected pulmonary complications will be followed:

- a. Upper respiratory infection (rhinitis, pharyngitis, otitis)
- b. Fungal pulmonary infection
- c. Viral pulmonary infection
- d. Bacterial pulmonary infection
- e. Mycobacterial pulmonary infection
- f. Pneumocystis carinii pneumonia
- g. Lymphoproliferative lung disease
- h. Other interstitial lung diseases
- i. Chronic obstructive lung disease
- j. Airway hyperreactivity
- k. Upper airway obstruction
- l. Pulmonary vascular disease

Criteria to diagnose these specific pulmonary complications are defined in Table 13.

We determined the frequency of specific tests by balancing the goal of early detection with cost and expected patient adherence. We recognized that frequent and invasive testing decreases patient adherence. The specific justification for each test and the rationale for the frequency of that test is addressed in the respective methods section and Table 14. Any studies already required and performed through other grants or contracts will be accessed and recorded to avoid duplication.

Table 13

Criteria for Diagnosis of Specific Pulmonary Complications

COMPLICATIONS	CRITERIA
a. Upper respiratory illness	Rhinitis, pharyngitis, or otitis diagnosed by appropriate history and physical examination.
b. Fungal pulmonary infection	Clinical evidence of pneumonia, new CXR abnormality, and tracheal secretion positive for fungal organism (by stain or culture).
c. Viral pneumonia	Clinical evidence of pneumonia, new CXR abnormality, and virus recovered from secretions, lavage fluid or lung biopsy without bacterial or PCP infection. Histologic evidence of invasive infection required for diagnosis of CMV.
d. Bacterial pneumonia	Clinical evidence of pneumonitis (i.e., cough, tachypnea, rales and purulent sputum) new chest x-ray abnormality, leukocytosis (>15,000 WBC predominant polymorphonuclear cells) with intracellular organisms from respiratory secretions or positive blood culture, or positive cold agglutinins.
e. Mycobacterial pulmonary infection	TUBERCULOSIS - New CXR abnormality, mycobacteria recovered from BAL or lung biopsy, or positive gastric aspirate. MAC - Detection of Mycobacterium avium-intracellular complex (MAC) by histologic assessment of biopsy or bronchoalveolar lavage fluid specimens; acid-fast organisms must be observed within recovered tissue alveolar (foamy) macrophages. Culture of these organisms from pleural fluid will also serve to define MAC infection of the lung.
f. Pneumocystis carinii pneumonia	Evidence of organisms from BAL fluid or open lung biopsy.
g. Lymphoproliferative interstitial lung disease	Evidence of interstitial lung disease by CXR and open lung biopsy histologically consistent for LIP or PLH (Joshi et al, 1985).
h. Other interstitial lung disease	Evidence of interstitial lung disease by CXR and pathology from open lung biopsy consistent with interstitial lung disease. BAL negative for PCP. (Edelson and Hyland, (1989)).
i. Chronic obstructive lung disease	Clinical findings, including expiratory airway obstruction on physical exam and/or chest roentgenographic evidence and evidence of hyperinflation in absence of clinical and/or laboratory finds of infection.
j. Airway hyperreactivity	Obstructive airway disease with clinical response to bronchodilators.
k. Upper airway obstruction	Abnormality by direct inspection and/or, appropriate clinical history.
l. Pulmonary vascular disease	Histologic evidence of open lung biopsy (Edelson and Hyland, 1989), or abnormality defined on cardiac catheterization or pulmonary angiography.
m. Bronchiolitis	Clinical findings consistent with bronchiolitis and absence of lobar

Rev. 11/01/94

Table 14
Schedule of Pulmonary Studies

Month Pt. On Study (± 1 mo.)	Questionnaires			Physical exam including RR	CXR	SpO2 (a) with heart rate	PFT (b)	BAL	Bx
	Form 41(c)	Form 42	Form 43						
0 - 1	I	I		ALL	I	ALL	I		
3	II		ALL	ALL	II	ALL			
6			ALL	ALL		ALL	ALL		
9			ALL	ALL		ALL			
12			ALL	ALL	ALL	ALL	ALL		
18			ALL	ALL	II	ALL	ALL		
24			ALL	ALL	I	ALL	I, IIa		
30			ALL	ALL	IIa	ALL	I, IIa		
36			ALL	ALL	I	ALL	I, IIa		
42			ALL	ALL	IIa	ALL	ALL		
48			ALL	ALL	I	ALL	ALL		
54			ALL	ALL	IIa	ALL	ALL		
60			ALL	ALL	I	ALL	ALL		
66			ALL	ALL	IIa	ALL	ALL		
72			ALL	ALL	I	ALL	ALL		
78			ALL	ALL	IIa	ALL	ALL		
Intercurrent Illness				ALL	ALL			(e)	(e)
Chronic lung disease				(d)	(d)			(f)	(f)

NOTE: I = Group I
II = Group II
IIa = Group IIa
ALL = Group I and II

- (a) ABG if SAT <96% or 96%-97% if clinically indicated.
- (b) Refer to Section 5.2.4.4. for details of PFT testing for specific age groups.
- (c) In addition, complete with any change in household.
- (d) As indicated.
- (e) Refer to Intercurrent Illness Algorithm (Figure 1).
- (f) Refer to Chronic Lung Disease Algorithm (Figure 2).

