2.2 Primary Hypotheses and Objective

Hypotheses

- H1. The incidence of cardiovascular* complications is elevated in the population of fetuses exposed to maternal HIV infection, who subsequently as infants are proved to have HIV infection.
- H2. The incidence of cardiovascular* and pulmonary** complications is elevated in the population of infants with vertically transmitted HIV-infection. The number of respiratory tract infections*** is also increased in this population.

Objective

- O1. To estimate the frequency of specific pulmonary** and cardiovascular* complications in children symptomatic with HIV-infection.

*, **, *** See Page 6

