5.4 Pathological Studies: Postmortem Examination of HIV-Infected Infants in Groups I and II

A number of infants and children in the study population will die each year. It is estimated that at least 50% of the P²C² HIV study patients who die will come to autopsy. Postmortem examination will provide important morphologic correlation with the antemortem functional assessments and clinical indicators. Consent for autopsy will be obtained in the customary manner for each institution using their standard hospital autopsy consent form. In those cases in which permission is obtained, the autopsy will be done in a timely fashion, generally within 24 hours of the demise of the patient. If there are no restrictions made in the consent given, a complete autopsy will be performed. A standard protocol will be used to ensure that appropriate cultures are performed, and that appropriate tissue is sampled and preserved for light microscopy, electron microscopy, and other special studies that may be done as ancillary studies.

[figure not shown]
The lungs will be prepared in a standard fashion by inflation fixation so that they will be suitable for morphometric assessment for correlation with clinical studies of pulmonary function as an ancillary study.

The heart will be carefully examined for structural malformations, chamber dimensions, ventricular wall and valve measurements according to a standard protocol so that appropriate tissues are retained for examination and ancillary studies.

Lesions of small and medium sized arteries have been described in the brain, kidneys, lungs, spleen, skeletal muscle, thymus, and small intestine. The brain was consistently involved. Apparently, larger musculoelastic arteries are not affected; however, it is not clear which such vessels have been examined in published reports. No arterial lesion was identified on gross examination and none could be seen radiologically. In order to examine the incidence and extent of arterial involvement in pediatric AIDS, arteries from various sites will be systematically examined in addition to evaluation of intraparenchymal vascular branches within the various organs.

Figure 8

EVALUATION OF PATIENTS WITH POSSIBLE SYMPTOMS RELATED TO THE HEART

6. Distributed Data Entry and Data Management

Figures 5 and 6 diagram the computer communication network, flow of study data, respectively. Various components of this system are described in detail in the following sections.

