8.2.6 Pathology Studies

Review of diagnostic biopsies, autopsies, and BAL fluid for consistency of diagnosis will be by a panel of three pathologists from the participating

institutions. When there is disagreement a consensus diagnosis will be made and data accordingly revised. Standardized methods with appropriate controls will be employed by all centers.

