APPENDIX II

Definitive Diagnostic Methods for Diseases Indicative of AIDS

Diseases	Definitive Diagnostic Methods
cryptosporidiosis cytomegalovirus isosporiasis Kaposi's sarcoma lymphoma lymphoid pneumonia or hyperplasia Pneumocystis carinii pneumonia progressive multifocal leukoencephalopathy toxoplasmosis	microscopy (histology or cytology).
candidiasis	gross inspection by endoscopy or autopsy or by microscopy (histology or cytology) on a specimen obtained directly from the tissues affected (in- cluding scrapings from the mucosal surface), not from a culture.
coccidioidomycosis cryptococcosis herpes simplex virus histoplasmosis	microscopy (histology or cytology), culture, or detection of antigen in a specimen obtained directly from the tissues affected or a fluid from those tissues.
tuberculosis other mycobacteriosis salmonellosis other bacterial infection	culture.

**HIV encephalopathy*
(dementia)**

clinical findings of disabling cognitive and/or motor dysfunction interfering with occupation or activities of daily living, or loss of behavioral developmental milestones affecting a child, progressing over weeks to months, in the absence of a concurrent illness or condition other than HIV infection that could explain the findings. Methods to rule out such concurrent illnesses and conditions must include cerebrospinal fluid examination and either brain imaging (computed tomography or magnetic resonance) or autopsy.

HIV wasting syndrome*

findings of profound involuntary weight loss >10% of baseline body weight plus either chronic diarrhea (at least two loose stools per day for ≥ 30 days) or chronic weakness and documented fever (for ≥ 30 days, intermittent or constant) in the absence of a concurrent illness or condition other than HIV infection that could explain the findings (e.g., cancer, tuberculosis, cryptosporidiosis, or other specific enteritis).

*For HIV encephalopathy and HIV wasting syndrome, the methods of diagnosis described here are not truly definitive, but are sufficiently rigorous for surveillance purposes.

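### Table 13, row f, does not count Pneumocystis pneumonia found only at autopsy, so its O1 frequency is slightly understated; adding autopsy lung as a coded source costs little

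*Protocol*

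**What the plan says.** Section 5.2 of the Protocol gives Table 13 its authority: "Criteria to diagnose these specific pulmonary complications are defined in Table 13". Row f, for PCP, reads in full "Evidence of organisms from BAL fluid or open lung biopsy". No row of Table 13 names autopsy tissue.

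The protocol treats autopsy as a separate kind of material:

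- Section 5.2.4.7 describes open lung biopsy as a surgical specimen about 1 cm on each side.
- Section 5.4 expects that at least 50% of "study patients who die will come to autopsy". It adds: "A standard protocol will be used to ensure that appropriate cultures are performed". The purpose it gives is correlation of morphology with findings in life.
- Section 8.2.6 says: "Review of diagnostic biopsies, autopsies, and BAL fluid for consistency of diagnosis will be by a panel of three pathologists". It continues: "When there is disagreement a consensus diagnosis will be made and data accordingly revised".

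PCP enters objective O1 (Section 2.2, frequency of specific complications) and O4 (Section 2.3, effect on lung function and life span). Section 7.1 also names it among the possible primary outcomes.

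**The concern.** A child whose lungs show Pneumocystis at autopsy, but who never had a diagnostic lavage or biopsy, has histologic proof of the disease and yet is not a case under row f. The protocol gives reasons why such children may exist. Section 3.1.3 describes an especially rapid course in the first year of life. Section 5.2.3.1 allows up to five days of empiric antibiotics before lavage or biopsy in hypoxemic children with focal consolidation.

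The error runs in one direction. Every uncounted child has died, so the O1 frequency of PCP can only be too low on this account. O4 is touched narrowly. Under Section 5.2.3.2, children with chronic lung disease have already been through the intercurrent-illness evaluation, so the gap opens only if such a child dies of a later PCP episode without diagnostic lavage or biopsy.

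**Working it through.** **The plan's own precision figure.** Section 4.2.2 uses a half-width of 100 × 1.96 × √(p(1−p)/n). For 25% of 200 Group I children this gives 100 × 1.96 × √(0.25 × 0.75/200) = 6.0, as stated.

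**Benchmark for this point.** Section 7.2 applies objectives about infected children to Groups I and IIa. Section 4.2 expects 200 and 120, so n = 320. O1 speaks of symptomatic children, whose number is not given, so 320 is itself an assumption. With the 24% PCP rate of Table 6:

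- expected cases: 0.24 × 320 = 76.8
- half-width: 100 × 1.96 × √(0.24 × 0.76/320) = 4.68 points

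**Cases that row f would drop.** Uncounted cases = D × A × P × U.

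| Input | Value | Source |
|---|---|---|
| D, deaths | 20 to 60 | assumed |
| A, share autopsied | 0.5 | Section 5.4, stated as a minimum |
| P, share of autopsies with Pneumocystis | 0.25 or 0.5 | 0.5 borrowed from Section 1 (children who died of AIDS by 1985); 0.25 assumed, since Section 3.1.3 reports better prognosis since then |
| U, share of these without lavage or biopsy | 0.2 to 0.5 | assumed |

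Results, with points = 100 × cases/320:

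- P = 0.25: 20 × 0.5 × 0.25 × 0.2 = 0.5 cases (0.16 points), up to 60 × 0.5 × 0.25 × 0.5 = 3.75 cases (1.17 points)
- P = 0.5: 20 × 0.5 × 0.5 × 0.2 = 1 case (0.31 points), up to 60 × 0.5 × 0.5 × 0.5 = 7.5 cases (2.34 points)

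**Effect on the reported rate.** The protocol does not say whether Table 6's 24% includes autopsy diagnoses.

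- If it does, row f would yield between (76.8 − 0.5)/320 = 23.8% and (76.8 − 7.5)/320 = 21.7%.
- If it does not, the fuller rate is between (76.8 + 0.5)/320 = 24.2% and (76.8 + 7.5)/320 = 26.3%.

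Every shift is smaller than 4.68 points. The formula covers autopsied children only. Deaths without autopsy stay unresolved under either wording of row f.

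**The case against.** **Scope.** Table 13 sits in a section on the evaluation of living children, and none of its tissue-based rows names autopsy. That can be read as a deliberate antemortem scope, with postmortem material handled in Sections 5.4 and 8.2.6. The panel review, with data revised after consensus, suggests that autopsy diagnoses reach the database, and the Manual of Operations and forms are not shown. This has some force. But Section 8.2.6 settles disagreement between readers and nowhere makes an autopsy finding a PCP case, so Table 13 remains the only stated rule.

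**Few children are exposed.** This stands. Section 5.2.3.1 sends hypoxemic children to lavage, preferably within 48 hours, and on to biopsy if lavage is non-diagnostic. Section 5.2.4.6 provides for lavage in intubated children. Section 4.2.3 counts at least one episode, so a child with an earlier proven episode is already a case.

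**An antemortem rule is defensible.** Autopsy depends on death and consent. An autopsy-only case has no known onset, and Section 7.1 makes time-to-event analysis the main type. This stands and shapes the fix.

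Three stronger readings are tempting but not supported:

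- *That the study loses its most severe PCP.* Fatal cases proven by lavage or biopsy count.
- *That the protocol contradicts the CDC definition in its Appendix 5*, which lists "microscopy (histology or cytology") as definitive for PCP without restricting the specimen. That definition is for surveillance and also accepts presumptive PCP. A stricter study criterion is a choice, not a contradiction.
- *That H2 is underpowered.* With 84 and 140 children, if 10% of a true 24% were missed, power would fall from 90% to 82%; at 5% missed, to 87%. The assumptions above imply 0.7% to 9.8% missed (0.5/76.8 to 7.5/76.8), and the upper end needs every input at its extreme. If the 24% already excludes autopsy cases, planned power is not reduced.

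**Conclusion.** The point holds as a small, one-directional understatement of the O1 frequency of PCP. Followed as written, row f excludes Pneumocystis proven only in autopsy lung, while the autopsies, cultures and pathologist review that could reveal it are already planned.

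The documents do not fix the size. About 0 to 2 points is plausible, inside the 4.7-point half-width, but this rests on assumed deaths and an assumed share never lavaged or biopsied. The one-half figure in Section 1 describes children infected with Pneumocystis, possibly diagnosed in life, and is not an autopsy-positivity rate. Section 5.4 also does not name Pneumocystis among its cultures. No stated sample size is wrong, and no conclusion is shown to change. This is a low-priority improvement, worth making because it is cheap.

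**What to change.** 1. Reword Table 13, row f, as: *Organisms identified in BAL fluid or in lung tissue from open biopsy or autopsy.* Code the source of each PCP diagnosis.
2. Report the O1 frequency with and without autopsy-only cases.
3. In O4 and all time-to-event analyses, keep the antemortem criterion (lavage or open biopsy) as the main analysis, and add autopsy-only cases as a sensitivity analysis. These cases have no known onset and occur only in children who died, so counting them in the main analysis would tie PCP to death by construction.

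The cost is one table row, one source code per diagnosis and one extra line in the O1 table, with no new procedure. The downside is that ascertainment then depends partly on death and on consent to autopsy, which is why the source code and the paired reporting are needed.

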5.2.1 Perinatal

The maternal history, prenatal and birth history, neonatal complications, and interventions are cofactors as listed in secondary hypotheses four and five. The perinatal form will be completed once on every patient and allow systematic collection of this information. We recognized that information will be obtained easily from Group II patients. Group I patients, especially those in foster care, may have missing data which will be handled appropriately during statistical evaluation of this form.

5.2.2 Scheduled Pulmonary Evaluation

The schedule of routine pulmonary evaluation is constructed to gather baseline data from patients prior to illness and to monitor the patients at an interval expected to allow early detection of pulmonary complications. The median age of diagnosis of HIV is 13 months, with the median age of onset of lymphoproliferative lung disease at 17 months. A relatively frequent interval of monitoring (every 3 months), will allow early detection of these pulmonary complications. Less invasive studies constitute this screening battery. Clinical illness prompts initiation of the algorithms for evaluation of an intercurrent illness or chronic lung disease. Questionnaires (Qst) were developed to follow the history of pulmonary symptoms, clinical course, and clinical care for Group I and Group II. The perinatal form is discussed in Section 5.2.1. The environmental Qst is completed at entry into the study and with each change of household during the study for both groups. The basic respiratory Qst is completed at entry into the study for Group I patients. The interval respiratory Qst is completed each visit following enrollment. During each patient's first year, the patient is seen every 3 months; during the remainder of this study, the patient is seen every 6 months. A physical examination form will be completed at all of these visits. The respiratory rate is always recorded during sleep or quiet breathing. Oxygen saturation (SpO₂) will be performed at every visit as outlined in Section 5.2.4.4. Pulmonary function testing will be performed biannually on Group I and II patients. Details of pulmonary function testing for specific age groups are found in section 5.2.4.4. A DTPA clearance scan will be performed on all patients at six-month intervals. Scans will be discontinued after 18 months in HIV negative patients (Group IIb). (DTPA studies were discontinued on February 10, 1993 on the recommendation of the Steering Committee).

5.2.3 Diagnostic Evaluation of Symptoms or Findings Suggestive of Lung Disease

All diagnostic evaluations will be performed in the Clinical Center. Procedures will follow the methods devised for purposes of the protocol (Section 5.2.4). The diagnostic evaluations may be triggered by the occurrence of symptoms, signs, abnormal laboratory tests, or chest x-ray (noted either at the time of a scheduled evaluation or between evaluations).

5.2.3.1 Intercurrent Illness

The patients being studied are at a high risk of developing significant

pulmonary problems. Therefore, any one of the following symptoms, signs and test results will trigger a respiratory evaluation:

1. Unexplained cough for more than 5 days
2. Oral temperature $> 38^{\circ}$ C for more than 5 days or rectal temperature $> 38.5^{\circ}$ C for more than 5 days
3. Tachypnea (See Section 5.2.4.1)
4. Oxygen saturation $< 96\%$
5. Abnormal chest x-ray
6. Crackles on auscultation
7. Appearance of digital clubbing

As part of the orientation and at each routine clinic visit, the caretaker of the subject will be alerted to the symptoms and instructed to contact the Clinical Center should they develop. If the patient is febrile with localizing extrapulmonary symptoms and no pulmonary symptoms, no further respiratory evaluation will take place. The patient will be contacted by telephone or visit after 48 hours to ascertain if the symptoms have resolved. If the patient remains symptomatic, he/she will be evaluated.

The respiratory symptom evaluation visit will include:

1. Interval visit questionnaire and physical examination
2. Chest radiograph (PA and lateral views)
3. Arterial blood gas
4. Blood culture
5. Respiratory cultures:
 - Adenovirus
 - RSV
 - Parainfluenza
 - Influenza (during the epidemic season)
6. Laboratory studies:
 - CBC, ESR, LDH, at each illness;
 - CD4/CD8, Serum IgG, serum frozen at -70° C (if none in previous two months)
7. Skin tests (if none in previous two months):
 - PPD
 - DHST
8. Cardiac physical examination, as required (see Section 5.3.8)

The intercurrent illness algorithm will be followed after the respiratory symptom evaluation visit (Figure 1). The algorithm is intended to maximize the possibility of making a diagnosis while minimizing invasive studies which might decrease patient adherence. If the symptom evaluation visit reveals a new abnormality on chest x-ray or tachypnea, further evaluation will be dependent upon presence or absence of hypoxemia. If a blood culture is positive with a new radiographic abnormality, the patient will be treated for a bacterial pneumonia with antibiotics. If a clinical response is not observed within 72 hours or if TMP-SMX is started, a bronchial lavage will be performed to rule out PCP. If the

patient remains symptomatic despite two weeks of appropriate antibiotic therapy, an open lung biopsy will be performed. We will wait up to five days after instituting empiric antibiotic therapy prior to performing a bronchial lavage or an open lung biopsy on patients with focal consolidation who are hypoxemic. An open lung biopsy will be performed within 24 hours if the radiograph shows diffuse interstitial lung disease with a negative BAL and the patient is hypoxemic.

Bronchoscopy/BAL

Patients will have bronchoscopy and bronchoalveolar lavage (BAL) according to the algorithm (Figure 1). BAL will be performed on hypoxemic patients or those unresponsive to appropriate treatment for up to 2 weeks or experiencing worsening symptoms. The fluid will be handled as per Section 5.2.4.6. The lavage should preferably be done within 48 hours of the documentation of hypoxemia or within 48 hours of starting TMP-SMX.

Open Lung Biopsy

An open lung biopsy will be done if a bronchial lavage is non-diagnostic or if treatment has failed despite a diagnostic bronchial lavage. The specimen will be processed as outlined in Section 5.2.4.7. All patients who undergo open lung biopsy for any reason will have a BAL the same day so that direct comparison of the value of these methods may be made and recommendations for their use in the future may be clarified.

Follow-up

Patients with intercurrent illness or chronic lung disease will continue to receive the scheduled follow-up after the illness has resolved or stabilized. In patients who are hospitalized, a discharge evaluation will be made. This will include:

- a) Physical examination
- b) Chest radiography
- c) Oxygen saturation and/or arterial blood gas

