Measurements of gas exchange are generally abnormal in adults with PCP and currently represent the best tests for distinguishing PCP from other causes of pulmonary deterioration (Stover et al, 1985; Stover and Meduri, 1988; Hopewell and Luce, 1985; Murray et al, 1984). The A-aDO₂ is usually elevated and is a sensitive indicator of PCP. This is especially true if the elevation is noted during exercise. In general, the degree of elevation is predictive of overall mortality. The diffusing capacity for carbon monoxide (DLCO) is also decreased, however, the decrease is not directly related to the quantity of PCP organisms in the lung (Stover and Meduri, 1988) and does not correlate with the A-a gradient for oxygen during exercise. This suggests that factors other than impaired diffusion affect gas exchange. The most likely explanation for the abnormality in gas exchange is a severe mismatching of ventilation and perfusion in the lung. In the infant, overall pulmonary blood flow is increased relative to lung mass (Feltz and Hansen, 1986) so even small changes in matching of ventilation and perfusion may result in an increase in the A-a gradient for oxygen. If this is the case, then the A-a gradient for oxygen may be a very sensitive indicator of early PCP infection.

Gallium 67 scanning has been studied extensively in adults with HIV infection and PCP. While an abnormal scan is a very sensitive index of parenchymal lung disease, it is not specific for PCP (Coleman et al, 1984). It has been suggested that HIV infected patients with PCP also have an increased uptake of 99Tc DTPA aerosols. This test is more attractive than Gallium scans in infants because the dose of radiation is lower and a second visit is not required. The sensitivity of this test for PCP in children is not known nor is its ability to distinguish PCP from LIP/PLH.

The definitive diagnosis of PCP requires identification of the organism in samples obtained from the tracheobronchial tree. Induction of sputum by inhalation of hypertonic saline is of use in adults if organisms are identified in the specimen (Clement et al, 1988). This test requires considerable cooperation and presently is of little use in children. In one study of 29 children with HIV infection, Bronchoalveolar lavage (BAL) correctly identified all 14 with PCP (Bye, Bernstein et al, 1987).

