5.2.3.2 Chronic Lung Disease (CLD)

Patients with CLD will first be identified with an intercurrent respiratory illness and will have had the evaluation outlined previously (intercurrent illness algorithm). The chronic lung disease algorithm will be followed for patients with an abnormal chest x-ray or tachypnea persisting for more than 2 weeks (Figure 2).

Cultures for CMV and EBV will be done if previously negative. Bronchoscopy and BAL will be performed on hypoxemic patients and normoxemic patients with increased tachypnea or deterioration in the chest radiographs over the 2 week period of observation. In those patients whose radiograph remains unchanged, the diagnosis of interstitial lung disease (LIP/PLH) is the most likely (Rubenstein, 1986). These patients will first have a BAL and, if negative, an open lung biopsy.

The CT scan should be performed in children with persistent infiltrate for six month duration, specifically persistent consolidation in one area of the lung. A CT scan can clearly delineate areas of bronchiectasis in these children and is encouraged in cases of persistent pneumonia when no specific diagnoses has been made.

Figure 1
Intercurrent Illness Algorithm

[figure not shown]
[figure not shown]

Figure 2
Chronic Lung Disease Algorithm

If the chest x-ray is unchanged or worse, or there is tachypnea or hypoxemia persisting for more than 2 weeks, the CLD algorithm will be followed. If the patient has a persistent infiltrate for six month duration, a thin-cut CT scan should be performed to diagnose bronchiectasis.

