5.2.4.7 Lung Biopsy Processing and Analysis

Rationale:

Lung biopsies will be done, whenever appropriate, (See Figures 1 and 2) to establish the diagnosis of the disease processes involving the lung. Infectious complications, although seen less in children than in the adult, are a frequent cause of morbidity and mortality. The biopsy findings, in addition to providing diagnostic information in each case, will provide information to the study concerning the relative frequency of infectious and non-infectious pulmonary complications. In addition to their diagnostic utility, systematic examination of lung biopsy tissue for the presence and location of such agents as EBV and CMV will help establish their role in the pulmonary lymphoproliferative lesions, seen almost exclusively in pediatric patients.

All patients who undergo open lung biopsy for any reason will have a BAL the same day so that direct comparison of the value of these methods may be made and recommendations for their use in the future may be clarified. (see Section 5.2.3.1)

Methods:

Open lung biopsy will yield a specimen approximately 1 X 1 X 1 cm. The biopsy should be obtained from an area of active disease as judged radiographically and in general should not be obtained from the tip of the lingula or the tip of the right middle lobe. There is considerable evidence in adults, less in children, that the changes in these areas are disproportionate and may lead to a faulty impression of the severity of the pathologic processes.

The biopsy will be divided for culture, light microscopy, electron microscopy and a portion will be frozen. The light microscopic sections will be examined with routine hematoxylin and eosin stains and with stain to identify organisms and structural elements. All biopsies will be processed such that portions will be suitably preserved for ancillary studies including examination for EBV, CMV, HIV, etc. by in situ and immunohistochemical methodology.

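### Same-day lavage and biopsy pairs come only from children who reach open biopsy, so they cannot support a general comparison of the two methods and probably understate lavage

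*Protocol*

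**What the plan says.** Section 5.2.3.1 (Open Lung Biopsy) gives the main rule: "An open lung biopsy will be done if a bronchial lavage is non-diagnostic or if treatment has failed despite a diagnostic bronchial lavage". The same section has two further triggers. One depends on lavage: "An open lung biopsy will be performed within 24 hours if the radiograph shows diffuse interstitial lung disease with a negative BAL" and the child is hypoxemic. The other names no lavage result: if the "patient remains symptomatic despite two weeks of appropriate antibiotic therapy, an open lung biopsy will be performed". For chronic lung disease with an unchanged radiograph, 5.2.3.2 says: "These patients will first have a BAL and, if negative, an open lung biopsy". Section 3.2.1 likewise describes open biopsy as held back for deteriorating patients whose lavage gave no diagnosis.

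Sections 5.2.3.1 and 5.2.4.7 both require that children biopsied for any reason "have a BAL the same day so that direct comparison of the value of these methods may be made", and both add that "recommendations for their use in the future may be clarified". Neither section says that the pairs come from a selected group.

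**The concern.** Entry to the paired comparison depends largely on how an earlier lavage turned out. A non-diagnostic lavage is itself a trigger for biopsy. A diagnostic lavage leads to biopsy only if treatment then fails. The children in whom lavage did its job, with a diagnosis made and a response to treatment, are absent from the pairs.

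The stated product is a recommendation on the future use of two procedures, one of them much more invasive. If the paired results are read as applying to every child who has lavage, selection alone could make lavage look worse. Section 3.2.1 cites a study of 29 HIV-infected children in which "Bronchoalveolar lavage (BAL) correctly identified all 14 with PCP". A poor same-day result here could seem to contradict that study with no real difference in the test.

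**Working it through.** The protocol states no sensitivity, sample size or power for this comparison, so there is no figure to reproduce. The steps below set out who enters, then the direction of the bias, then what can still be estimated.

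**1. Who enters the pairs**

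- Non-diagnostic or negative lavage (5.2.3.1, 5.2.3.2): enters.
- Diagnostic lavage, treatment failed (5.2.3.1): enters.
- Symptoms persisting after two weeks of antibiotics (5.2.3.1): enters, with no lavage result named.
- Diagnostic lavage, treatment worked: no route in the text.

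**2. Direction and size of the bias (illustration; all inputs assumed)**

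Among children who have the disease, let

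- s = sensitivity of one lavage
- f = share biopsied after a diagnostic first lavage
- g = share biopsied after a non-diagnostic first lavage
- c = chance that the same-day lavage simply repeats the first result; otherwise it is a fresh draw with probability s.

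The share of biopsied cases with an earlier diagnostic lavage is w = s·f / [s·f + (1−s)·g].

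Apparent same-day sensitivity = w·[c + (1−c)s] + (1−w)·(1−c)s = (1−c)s + c·w.

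So bias = c·(w − s). It is negative when c > 0 and w < s, and w < s exactly when f < g. It is zero if c = 0 or f = g.

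With s = 0.90, g = 1, f = 0.1: w = 0.09/(0.09 + 0.10) = 0.474. At c = 0.5, apparent sensitivity = 0.45 + 0.237 = 0.69.

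| f | w | c = 0 | c = 0.5 | c = 1 |
|---|---|---|---|---|
| 0 | 0 | 0.90 | 0.45 | 0.00 |
| 0.1 | 0.47 | 0.90 | 0.69 | 0.47 |
| 0.3 | 0.73 | 0.90 | 0.82 | 0.73 |

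The row f = 0 is a limiting case that the protocol does not describe, since it does biopsy treatment failures. Over s = 0.70 to 0.95 and f = 0.1 to 0.3, with g = 1 and c = 0.5, apparent sensitivity runs from 0.45 to 0.90. The model leaves out any effect of treatment on the repeat lavage.

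**3. Do the protocol's rules imply f < g and c > 0?**

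f < g follows from the rules unless nearly every lavage-diagnosed child fails treatment. For c no figure is given. Some agreement is plausible, because Table 13 requires open biopsy histology for lymphoproliferative and other interstitial lung disease. Lavage cannot establish these diagnoses on either occasion. Section 5.2.3.2 calls LIP/PLH the likeliest diagnosis when the radiograph is unchanged.

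**4. What can be recovered for PCP**

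Table 13 accepts organisms from lavage fluid or from open biopsy, so a positive lavage needs no biopsy to count as a case. Assume 50 PCP cases and s = 0.90: the first lavage finds 45 and misses 5. If all 5 are biopsied and identified, first-lavage sensitivity = 45/(45 + 5) = 90%, the assumed value.

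If only 70% of lavage-negative children are biopsied, the crude figure is 45/(45 + 3.5) = 93%. Weighting the biopsy-found cases by 1/0.7 restores 45/(45 + 5) = 90%, provided those biopsied represent all lavage-negative children.

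**The case against.** Three stronger readings are tempting, and the documents do not support them.

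- A reader might infer that only lavage failures are compared. The main rule also admits treatment failure after a diagnostic lavage, and the persistent-symptom trigger names no lavage result. In the illustration, 47% to 73% of biopsied cases had an earlier diagnostic lavage. Figures 1 and 2, which 5.2.4.7 cites for when biopsy is appropriate, are not shown in the text at hand, so the list of routes may be incomplete.
- A reader might infer that no analysis can repair the selection. For PCP, step 4 shows otherwise.
- A reader might quote a definite size. Take 5 missed cases and 4.5 treatment failures (10% of 45) at biopsy, with same-day positivity q in the missed cases and 70% in the failures. Apparent sensitivity is then (5q + 3.15)/9.5, or 33% at q = 0 and 81% at q = 0.9. With 90% in both groups it is (4.5 + 4.05)/9.5 = 90%, with no bias. These inputs are all assumed.

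The best defence of the protocol is that it speaks of the value of the methods and not of sensitivity, and that the added value of biopsy in children who reach it is a fair question. The comparison is also in none of H1–H7 or O1–O4, and lavage and biopsy are not among the diagnostic methods that 7.2 lists for O2. This limits the weight of the point and means the pairs should be kept. It does not remove the point, because both sections link the pairs to recommendations for future use without limiting them to biopsied children.

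**Conclusion.** The point holds in a limited form. Same-day pairs describe children who reach open biopsy, selected mainly for a non-diagnostic earlier lavage or for treatment failure. They cannot be carried over to all children who have lavage.

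The likely direction is against lavage. This rests on two conditions: a non-diagnostic lavage leads to biopsy more often than a diagnostic one, which the rules imply, and the repeat lavage tends to agree with the first, which is plausible but not quantified. The size cannot be fixed from the documents. It is nil if the two lavages are independent and treatment does not alter the repeat result.

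The consequence is confined to a secondary conclusion. No numbered hypothesis, objective or sample size depends on it.

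**What to change.** In 5.2.3.1 and 5.2.4.7, base general recommendations on two quantities:

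- (a) the diagnostic yield of the first lavage among all lavaged children
- (b) the added yield of biopsy after a non-diagnostic first lavage.

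For PCP, (a) and (b) together give first-lavage sensitivity under the Table 13 definition, if lavage-negative children are biopsied as planned. The number not biopsied should be reported. Cases missed by both methods stay uncounted.

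Report the same-day pairs as describing biopsied children only. Separate them by route (non-diagnostic lavage or treatment failure), and show any child with no earlier lavage on a separate line. Separate them also by diagnosis, because Table 13 requires biopsy histology for lymphoproliferative and other interstitial disease. The pairs may still inform statements about children who reach biopsy.

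Nothing changes in when lavage or biopsy is done. The cost is extra tabulation, a rewording of two paragraphs and a narrower claim.
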